8.1.1. Primary Estimand

[figure not shown]

8.1.2. Overall Summary of Adverse Events

An overall summary of TEAEs will be summarized by treatment group and treatment cycle by providing the number and percent of patients who experience the following:

An overall summary of the number and percentage of patients with at least one TEAE will be presented by SOC and PT. At each level of patient summarization, a patient is counted once if the patient reported one or more events starting in each treatment group in each treatment cycle, and across all cycles (by overall total doses of low, medium, and high). Percentages will be calculated out of the number of patients in the SAF. The table will be sorted by SOC and PT in descending order of incidence from the SOC and PT with the highest total incidence to the SOC and PT with the lowest total incidence. Summaries and listings will be presented for the SAF.

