4.1. General considerations

The statistical principles applied in the design and planned analyses of this study are consistent with International Council for Harmonisation (ICH) E9 guidelines (ICH 1998). All descriptive summaries will be presented by dose group, treatment cycle and nominal visit/timepoint (where applicable).

All efficacy analyses will be based upon the modified Full Analysis Set (mFAS, Section 4.5.2), and all safety as well as demographic and baseline characteristic analyses will be based upon the Safety Analysis Set (Section 4.5.3). Summary of safety and efficacy analyses will be displayed by treatment group and treatment cycle. Additional analyses will be performed on selected populations as specified in the sections below.

Unless otherwise stated, the following methods will apply:

• Treatment groups: For a given assessment or event, treatment group will be assigned to a patient based on the last dose received as follows:

Range	of total dose	treatment group
a.	Non-missing dose ≤ 200 units	ABP-450 150 units
b.	> 200 to ≤ 300 units	ABP-450 250 units
c.	> 300 units	ABP-450 350 units

In addition, three dose groups (low, medium, high) based on total dose across the whole study will be assigned to a patient for a given assessment or event as follows:

Rang	e of overall total dose	Overall treatment group
a.	Non-missing dose ≤ 800 units	ABP-450 low
b.	$> 800 \text{ to} \le 1200 \text{ units}$	ABP-450 medium
c.	> 1200 units	ABP-450 high

- Continuous variables: will be summarized using summary statistics (i.e., non-missing values (n), mean, standard deviation, median, minimum, and maximum). For the summary statistics of all continuous data, minimum and maximum values will be displayed to the same level of precision as reported, unless otherwise specified. Mean and median will be displayed to one level of precision greater than the data collected. Standard deviation will be displayed to two levels of precision greater than the data collected.
- Categorical variables: will be described using the patient count and percentage in each category. When counts are presented, in cases where the count is zero, the percentage will

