not be displayed to draw attention to the non-zero counts. A row denoted 'Missing' will be included in count tabulations where specified on the shells to account for missing values. The denominator for all percentages will be the number of populated patients in that treatment within the analysis set of interest, unless otherwise specified. Frequency statistics will be displayed using one decimal place except for the display of 100% frequency which will be displayed as 'XX (100)'.

- Rules for multiple assessments: To summarize data collected over time, summary tables will be presented by scheduled visit. Unscheduled visits may be included in specific summaries (such as worst post-baseline measurement) and will be described in the relevant sections. Both scheduled and unscheduled visits will be included in the data listings.
- Date and time display conventions: The following display conventions will be applied in all outputs where dates and/or times are displayed:

Date only: DDMMMYYYY

Date and time: DDMMMYYYY HH:MM

Partial dates will be listed as such (i.e., where day or day and month is missing, only MMMYYYY or YYYY will be displayed, respectively).

- Multiple comparisons: There will be no statistical adjustment for multiplicity.
- Treatment terminology and order to be used in TLF outputs:
 - Unless specified, the following labels will be used for summary tables:
 - a. ABP-450 150 units
 - b. ABP-450 250 units
 - c. ABP-450 350 units
 - For summary of disposition, demography, medical history, prior medications, and first secondary estimand, the following will be used:
 - a. ABP-450 low
 - b. ABP-450 medium
 - c. ABP-450 high

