4.2. Key Definitions

The following key definitions will be used:

• Study Day: Within each treatment cycle, the study day of an event is defined as the relative day of the event starting with the date the study drug administration (reference date) for that Cycle as Study Day 1 (there will be no Day 0 for analysis purposes). The study day of events occurring before the first study drug administration in the first treatment cycle will be calculated as:

Study Day = (date of event – date of first study drug administration).

For events occurring on or after Study Day 1 in the first treatment cycle (including protocol specified Day 0 "rollover" visit), study day will be calculated within cycles as:

Study Day = (date of event/visit within a cycle – Date of study drug administration of that cycle) + 1.

Study days will only be calculated for events with complete or imputed dates and will be undefined for events that are "ongoing" at the end of the study.

- Baseline: The last observation on or before date of first dose in the ABP-19000 study will be considered as the baseline measurement unless otherwise specified. Repeat or unscheduled assessments may be included in the derivation of the baseline value.
- Change from baseline: The change from baseline value is defined as the difference between the result collected/derived at a post-baseline visit/timepoint within a cycle and the baseline value. The change from baseline value at each post-baseline visit/timepoint within a Cycle will be calculated for all continuous parameters using the formula:

Change from baseline Value = Result at Visit or Timepoint within a cycle– Baseline Value

The change from baseline value will only be calculated if the specific post-baseline visit/timepoint within a treatment cycle results and the baseline value for the parameter are both available and will be treated as missing otherwise.

All analyses will be conducted using

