4.5.3. Safety Analysis Set (SAF)

The SAF will consist of all patients who received at least one dose of the investigational study drug. The SAF will be used to tabulate all safety data excluding the primary estimand.

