8.1.5. Severity of Adverse Event

The severity or intensity of an AE refers to the extent to which an AE affects the patient's daily activities. The severity of the AE will be rated as mild, moderate, or severe. Changes in the severity of an AE will be captured in the CRF. The incidence of TEAEs will be tabulated by SOC and PT and severity by treatment group within each treatment cycle. Incidence will be based on the worst severity within each level of summarization.

Listings will be presented for the SAF.

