8.1.7. Adverse Events Leading to Treatment Discontinuation

Incidence of TEAEs with a study drug action taken as "Drug Withdrawn" will be summarized by SOC and PT by treatment group within each treatment cycle as described in Section 8.1. At each level of patient summarization, a patient is counted once if the patient reported one or more events. Percentages will be calculated out of the number of patients in the SAF.

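### SAP 8.1.2 tabulates TEAEs by dose group within cycle but gives the SAF count as denominator; read literally, non-zero percentages print too low, and the SAP 4.1 default does not fully cure this.

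*SAP*

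**What the plan says.** The SOC/PT paragraph printed under SAP 8.1.2 (it may belong to 8.1.3, whose heading is not visible) defines the count this way: "a patient is counted once if the patient reported one or more events starting in each treatment group in each treatment cycle". It adds across-cycle columns by overall low, medium and high dose. The denominator follows: "Percentages will be calculated out of the number of patients in the SAF". The paragraph closes by separately naming the SAF as the set for its summaries and listings.

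SAP 8.1.7 uses the same layout, in that discontinuation TEAEs "will be summarized by SOC and PT by treatment group within each treatment cycle as described in Section 8.1", and repeats the denominator sentence. SAP 8.1.8, on study withdrawal, does the same.

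The definitions that bear on this are:

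- SAP 4.5.3: "The SAF will consist of all patients who received at least one dose of the investigational study drug". The set is not split by dose or cycle.
- SAP 4.1, default: "The denominator for all percentages will be the number of populated patients in that treatment within the analysis set of interest, unless otherwise specified". Cycle is not mentioned.
- SAP 4.1, grouping: "For a given assessment or event, treatment group will be assigned to a patient based on the last dose received". A patient can therefore change group between cycles.
- SAP 4.2: study day is counted within each cycle, "starting with the date the study drug administration (reference date) for that Cycle as Study Day 1". A cycle thus begins with its own injection.
- SAP 3.4 leaves retreatment to the investigator, and SAP 4.5.4 defines the SAFR by removing SAF patients who were never retreated. The plan thus allows later cycles to hold fewer patients than the SAF.

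**The concern.** Numerator and denominator describe different populations. Only patients injected in a given cycle, at a dose in a given group, can contribute an event to that cell. A denominator of all SAF patients also includes those not injected in that cycle and those injected at another dose level. The printed percentage then reflects how many patients were in the cell as well as how often they had events.

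The primary objective is the safety of repeat injections, and these tables show TEAEs by dose and by cycle. A reader would take a percentage in a cycle-by-dose cell as the incidence among patients treated there. On the literal reading it is not that, and percentages cannot be compared between cells of different size.

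**Working it through.** The documents state no TEAE percentage and no cell sizes, so there is no figure of the plan's own to reproduce. The check is direct arithmetic on the stated denominator.

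**Inputs.** SAP 4.3 puts potential enrolment from the parent study at about 59, and protocol 7.2 at about 60. I take the SAF as 59; this is an assumption, since it is a number who might enrol and not a SAF count. All cell sizes and event counts below are also assumed.

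**Formulas.** Let x be the patients with an event in a cell, n the SAF patients treated in that group and cycle, and N the SAF size.

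- Percentage among those treated in the cell: 100 × x/n.
- Percentage on the literal reading: 100 × x/N.
- Ratio of the second to the first: n/N. It is below 1 unless every SAF patient falls in that one cell. Under SAP 4.1 no percentage is shown for a zero count, so only non-zero cells are affected.

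**Single cell, n = 12 and x = 3.** 3/12 = 25.0%. Literal: 3/59 = 5.1%, a factor of 12/59 = 0.203. With N = 60 the literal figure is 3/60 = 5.0%; with N = 45 it is 3/45 = 6.7%.

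**Range of cell sizes, 20% incidence, N = 59.**

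| n | x | x/n | x/59 | factor n/59 |
|---|---|---|---|---|
| 40 | 8 | 20.0% | 13.6% | 0.68 |
| 30 | 6 | 20.0% | 10.2% | 0.51 |
| 20 | 4 | 20.0% | 6.8% | 0.34 |
| 10 | 2 | 20.0% | 3.4% | 0.17 |
| 5 | 1 | 20.0% | 1.7% | 0.08 |

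**Across-cycle columns.** With 20 patients in an overall dose group and 8 affected, 8/20 = 40.0% prints as 8/59 = 13.6%.

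**Softer reading.** Suppose the sentence only names the analysis set and the SAP 4.1 default supplies the column denominator. The across-cycle columns are then correct, because the overall group is the denominator. The by-cycle columns are not settled. The default counts patients in a treatment without reference to cycle, while group membership follows the last dose and retreatment is discretionary. If it is programmed as everyone ever in the group, say 25 patients (assumed), the cell of 12 with 3 affected prints as 3/25 = 12.0%, still below 25.0%. If it is programmed per cycle, it prints 25.0%. The visible text does not say which.

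**The case against.** The best reply is that SAP 4.1 and 8.1.2 fit together without conflict: 4.1 asks for patients in that treatment within the analysis set, and 8.1.2 names the set. Nothing in 8.1.2 says that dose group is to be ignored. Part of this stands. The text is ambiguous, and a reader who infers that the tables will certainly be wrong goes too far. Text is missing from 8.1, the table shells are not available, and either may already give a cycle-specific n. The reply does not dispose of the point, for two reasons. The default yields to any other specification, and the 8.1.2 paragraph names the SAF a second time as its analysis set, so the denominator sentence is fairly read as doing more than that. And the softer reading still leaves the cycle restriction unwritten.

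Three stronger inferences are tempting and not supported:

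- **That the printed percentages would reverse the dose order or create a trend across cycles.** This needs particular cell sizes, and the documents give none.
- **That the 8.1.2 table would contradict the severity table in 8.1.5.** That section says "The incidence of TEAEs will be tabulated by SOC and PT and severity by treatment group within each treatment cycle" and states no denominator. Any figure for it would assume a cycle rule that 4.1 does not visibly contain.
- **That 8.1.7 is a firmer error than 8.1.8.** Stopping study drug, like leaving the study, ordinarily happens once per patient. A share of all treated patients is a valid quantity in both, if labelled so.

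The reply that little hangs on this also has force. SAP 4.3 plans no comparative analyses, counts appear beside percentages (SAP 8.1), and SAP 7.2.1 plans exposure by cycle and group, so a reader could recompute the rates. The primary estimand uses the SAFR, and this point does not extend to it.

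**Conclusion.** Wrong as written, of low to moderate importance. The 8.1.2 paragraph defines cells by group and cycle and states a denominator that, taken at its word, is the whole SAF. Each non-zero percentage is then too low by the factor n/N: 5.1% instead of 25.0% for 3 of 12, on an assumed SAF of 59. Under the softer reading the across-cycle columns are right, but later-cycle percentages would still be too low where patients are not retreated or change dose group, unless the programmer adds a restriction that is not in the visible text. The size of the error in the real tables cannot be known from the documents, because it depends on cell sizes they do not give. The counts are correct on either reading. The conclusion is that the denominator must be stated, not that the safety results are unreliable.

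**What to change.** - **SAP 8.1.2 (or 8.1.3, if the paragraph belongs there).** Replace the denominator sentence with wording such as: for each cycle and treatment group, percentages are based on the SAF patients who received ABP-450 in that cycle and are in that group for that cycle, with this n in the column header. For across-cycle columns, use the number of SAF patients in each overall dose group.
- **SAP 4.1.** Add the cycle-specific denominator to the default, so that every by-cycle table without a denominator of its own follows it.
- **SAP 8.1.7 and 8.1.8 alike.** Use the same denominator, or keep the whole SAF only if the table is labelled as the share of all treated patients.
- **Footnote to by-cycle tables.** Say that later cycles describe only patients who were retreated, at the investigator's discretion, so patients who had adverse events may be under-represented there.

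If the shells already carry a cycle-specific n, the SAP text need only be aligned with them. The cost is wording and table programming; no new data are needed, since exposure by cycle and group is already planned. The downside is that late-cycle percentages will rest on small n, which the column header makes visible.

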8.1.4. Relationship of Adverse Events to Study Drug

Summaries of TEAEs related to ABP-450 will be presented by SOC and PT in descending order of frequency by treatment group within each treatment cycle. Summaries for TEAEs related to

ABP-450 will be presented using patients in the SAF who received at least one dose of ABP-450. Data will be listed for the SAF.

8.1.5. Severity of Adverse Event

The severity or intensity of an AE refers to the extent to which an AE affects the patient's daily activities. The severity of the AE will be rated as mild, moderate, or severe. Changes in the severity of an AE will be captured in the CRF. The incidence of TEAEs will be tabulated by SOC and PT and severity by treatment group within each treatment cycle. Incidence will be based on the worst severity within each level of summarization.

Listings will be presented for the SAF.

8.1.6. Serious Adverse Events

Treatment-emergent SAEs will be presented by SOC and PT in a manner similar to that described in Section 8.1. Incidence and frequency summaries and listings of all treatment-emergent SAEs will be presented for the SAF by treatment group in each treatment cycle, and across all cycles (by overall total doses of low, medium, and high).

8.1.7. Adverse Events Leading to Treatment Discontinuation

Incidence of TEAEs with a study drug action taken as "Drug Withdrawn" will be summarized by SOC and PT by treatment group within each treatment cycle as described in Section 8.1. At each level of patient summarization, a patient is counted once if the patient reported one or more events. Percentages will be calculated out of the number of patients in the SAF.

8.1.8. Adverse Events Leading to Study Withdrawal

Summaries of incidence of TEAEs leading to study withdrawal will be tabulated by SOC and PT for each treatment group within each treatment cycle as described in Section 8.1. Percentages will be calculated out of the number of patients in the SAF.

8.1.9. Suspected Unexpected Serious Adverse Events

A suspected unexpected serious adverse event (SUSAR) is defined as an AE, the nature or severity of which is not consistent with the applicable product information (e.g., investigator's brochure for an unapproved investigational medicinal product). The incidence of SUSARs will be summarized by SOC, PT, and treatment group for each treatment cycle.

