6.2.1.2 Serious Adverse Events

An SAE is defined as any event that

- results in death
- is immediately life-threatening
- requires inpatient hospitalization or prolongation of existing hospitalization
- results in persistent or significant disability/incapacity
- is a congenital anomaly/birth defect

Adverse events will be assessed from the time the patient signs the ICF until exit from the study (ie, 52 weeks or end of treatment [ET] after Day 0 "rollover").

Serious AEs that occur more than 56 days (ie, 8 weeks) after the last dose of investigational study drug and the patient has exited the study need not be reported unless the investigator considers them related to investigational study drug.

At every study visit, patients will be asked a standard non-leading question to elicit any medically related changes in their well-being. They will also be asked if they have been hospitalized, had any accidents, used any new medications, or changed concomitant medication regimens (both prescription and over-the-counter medications).

In addition to patient observations, AEs identified from any study data (eg, laboratory values, physical examination findings, changes in 12-lead ECG results) or identified from review of other documents that are relevant to patient safety will be documented on the AE page in the eCRF.

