6.2.1.5 Reporting Serious Adverse Events

Sponsor or its designee is responsible for reporting relevant SAEs to the competent authority, other applicable regulatory authorities, and participating investigators, in accordance with the ICH guidelines and/or local regulatory requirements.

The sponsor is responsible for reporting unexpected fatal or life-threatening events associated with the use of investigational study drug (expedited reports) to the regulatory agencies and competent authorities by telephone or fax within 7 calendar days after being notified of the event. The sponsor should report other relevant SAEs associated with the use of investigational study drug to the appropriate competent authorities (according to local guidelines), investigators, and the institutional review board (IRB) by a written safety report within 15 calendar days of notification.

6.2.1.6 Suspected Unexpected Serious Adverse Reactions and Non-Serious Adverse Events of Special Interest

The sponsor will promptly evaluate all suspected unexpected serious adverse reactions (SUSARs) and non-serious AEs of special interest against cumulative investigational study drug experience to identify and expeditiously communicate possible new safety findings to investigators, IRBs/independent ethics committees (IECs), and applicable health authorities based on applicable legislation.

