8.1. Adverse Events

AEs will be collected from the time of signing of the ICF until 52 weeks or end of treatment after Day 1 "rollover" (exit from the study). All AEs will be classified by SOC and PT according to the MedDRA, version 24.0 or later.

Serious AEs that occur more than 56 days (i.e., 8 weeks) after the last dose of investigational study drug and the patient has exited the study may be reported if the investigator considers them related to investigational study drug.

[figure not shown]
The severity or intensity of an AE refers to the extent to which an AE affects the patient's daily activities. Adverse event severity will be classified as "Mild", "Moderate", and "Severe". TEAEs with missing severity will be imputed as 'Severe'.

The investigator will provide an assessment of the relationship of the event to the trial drug. The possible relationships are "Unrelated", "Possibly Related", "Probably Related" and "Definitely Related". Any TEAE reported as "Definitely Related", "Possibly Related" or "Probably Related" will be considered related to the ABP-450. TEAEs that are missing a relationship will be counted in the summary table as "Definitely Related" but will be presented in the data listing with a missing relationship.

Treatment emergent adverse events (TEAEs) are defined as those AEs that started on or after the day of first dose of ABP-450 up to 5 days after the end of treatment or end of study visits. Only TEAEs will be included in the AE summary tables. However, all adverse events will be listed and TEAEs will be flagged.

[figure not shown]
The TEAEs will be summarized by SOC and PT and will include the number and percentage of patients experiencing an event and the number of events (based on start date of the event) by treatment cycle and treatment group. Patients will be counted only once for each SOC and PT level (categorical descriptive analyses). In general, TEAE summary tables will be sorted by SOC and PT in descending order of frequency from the SOC and PT with the highest total frequency to the SOC and PT with the lowest total frequency.

For the purpose of inclusion in TEAE tables, incomplete AE onset and end dates will be imputed following date imputation guidelines (see Section 13.2).

[figure not shown]

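### SAP 8.1.9 defines a SUSAR by unexpectedness alone, leaving out the seriousness and suspected causality that its own label and the protocol's term require

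*SAP*

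**What the plan says.** SAP 8.1.9 introduces the term as "A suspected unexpected serious adverse event (SUSAR") and says that it "is defined as an AE, the nature or severity of which is not consistent with the applicable product information". The investigator's brochure is given as an example of that information. The section then plans the output: "The incidence of SUSARs will be summarized by SOC, PT, and treatment group for each treatment cycle". It states no other condition for entering the table.

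Protocol 6.2.1.6 uses a slightly different term, "suspected unexpected serious adverse reactions (SUSARs"), and has the sponsor evaluate these events promptly against cumulative experience with the drug. The visible protocol text does not define the term further.

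Two rules elsewhere bear on the missing conditions. Protocol 6.2.1.2 gives the seriousness criteria, opening with "An SAE is defined as any event that" and listing outcomes such as death and hospitalization. SAP 8.1 says that events rated possibly, probably or definitely related "will be considered related to the ABP-450". SAP 8.1.9 refers to neither.

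**The concern.** The term has three parts: suspected causality, unexpectedness and seriousness. In a SAP, the sentence that says how something is defined is normally the derivation rule, and this one gives a single part. Two competent programmers could build different tables, one from the label and one from the definition.

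What is at stake is the meaning of a table with a regulatory label. Protocol 6.2.1.6 treats SUSARs and non-serious events of special interest as separate categories. Under the literal SAP rule, an unexpected non-serious event could be reported as a SUSAR. The report could then show SUSARs that the sponsor never evaluated as such. The study also has no independent safety committee (protocol 6.4) and no data monitoring committee (protocol 11.1.1), so the end-of-study safety tables need to be unambiguous.

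**Working it through.** The plan states no figure on this point, so there is nothing to reproduce. The check is whether each part of the term is present in the definition or supplied by other text.

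| Part of the term | In the SAP 8.1.9 label | In the SAP 8.1.9 definition | Available elsewhere | Linked from 8.1.9 |
|---|---|---|---|---|
| Unexpected | yes | yes | – | – |
| Serious | yes | no | protocol 6.2.1.2 | no |
| Suspected causality | yes | no | SAP 8.1 relatedness rule | no |

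**Does *severity* in the definition supply seriousness?** No. SAP 8.1 says: "The severity or intensity of an AE refers to the extent to which an AE affects" the patient's daily activities, and grades it mild, moderate or severe. That is intensity. Seriousness is the separate outcome list in protocol 6.2.1.2. A mild event of an unlisted type is inconsistent with product information in its nature, and so meets the definition.

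**Does a general rule for adverse event tables supply either part?** The visible general filter in SAP 8.1 limits the summary tables to treatment-emergent events. It imposes no seriousness or causality condition.

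**Does the protocol's term help?** It ends in *reactions*, which implies causality. The SAP replaces this with *event* while keeping the acronym, so the word that carries causality most directly is lost. *Suspected* remains in the SAP label but not in the definition.

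**Test cases**, all treatment-emergent:

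| Event | Literal definition | All three parts required |
|---|---|---|
| Unexpected, non-serious, unrelated | counted | not counted |
| Unexpected, non-serious, related | counted | not counted |
| Unexpected, serious, unrelated | counted | not counted |
| Unexpected, serious, related | counted | counted |
| Expected, serious, related | not counted | not counted |

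The two readings differ in three of the five rows, always towards more events under the literal reading. One event of any of those three kinds is enough to make the tables differ.

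**Which inputs exist?** The visible list of adverse event data in protocol 6.2.1.4 includes seriousness and the investigator's assessment of relationship. It has no expectedness item, so that part must come from another source.

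**The case against.** The strongest reply is that this is loose drafting. The heading and the defined term still say *suspected* and *serious*, and the next section, SAP 8.1.10, is headed as covering non-serious events of special interest. On that view the sentence only explains *unexpected*, and nobody would put mild, unrelated events in a table titled as serious. Expectedness is also not among the visible collected fields, so the table may in practice be filled from the sponsor's own SUSAR determinations, and then no over-count arises. This stands in part. It means the over-count is possible rather than certain. It does not remove the defect, because no visible text tells the programmer to use the label or a sponsor determination instead of the written definition.

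Three stronger inferences are tempting, and the documents do not support them.

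- **That true SUSARs would be hidden.** Treatment-emergent serious events have their own summaries and listings (SAP 8.1.6), related events are summarised separately (SAP 8.1.4), and all adverse events are listed (SAP 8.1). A true SUSAR would still be visible there.
- **That the primary safety result is affected.** Protocol 7.5.1 summarises the proportion of patients with treatment-related serious events in the retreated set, without using the SUSAR definition. Expedited reporting is governed by protocol 6.2.1.5, not by this table.
- **That the number of miscounted patients can be stated.** Neither document gives a rate of unexpected events, so any count would be a guess.

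The conflict with the protocol is also inferred from its term, since the visible protocol text gives no full SUSAR definition.

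**Conclusion.** The point holds as a definitional error of limited reach. SAP 8.1.9 is wrong as written: its definition omits two of the three conditions in its own label and in the protocol's term. If the definition is followed literally, the SUSAR table could include non-serious or unrelated unexpected events and disagree with the sponsor's evaluation under protocol 6.2.1.6.

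The effect is confined to one descriptive table, and its size cannot be derived from the documents. The conclusion assumes that no blacked-out text or missing figure in SAP 8.1 adds the two conditions. That could not be checked, but the definition sentence itself is complete. The correction is cheap and should be made before the table is produced.

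**What to change.** Redefine a SUSAR in SAP 8.1.9 as a treatment-emergent adverse event that meets all three conditions:

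- serious under the criteria in protocol 6.2.1.2;
- related to ABP-450 under the SAP 8.1 rule (possibly, probably or definitely related);
- unexpected in nature or severity against the applicable product information.

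Replace *event* with *reaction* in the term and heading, as in the protocol. State that expectedness is taken from the sponsor's or pharmacovigilance SUSAR determination, because the visible adverse event fields do not include it.

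Then reconcile the table with the sponsor's safety data. Two rules in SAP 8.1 could produce legitimate differences that should be explained. Events with a missing relationship are counted in the summary table as definitely related. Related serious events reported after study exit may fall outside the treatment-emergent window, which closes 5 days after the end-of-treatment or end-of-study visit.

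The cost is one or two SAP sentences and that reconciliation. Seriousness and relationship are already collected, so no new patient data are needed.
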